2.8.5.4 Resource utilization

Data relating to resource utilization will be used for the purpose of economic evaluation and will be carried out and reported as a separate activity.

[figure not shown]
2.11 Biomarkers

[figure not shown]
2.11.1 Chronic Urticaria (CU) index panel

[figure not shown]
The CU index panel consists of the CU Index[®], thyroid peroxidase IgG and thyroglobulin IgG assays. CU index assessed at V201 will be summarized as part of baseline characteristics (see section 2.3). Thyroid peroxidase IgG and thyroglobulin IgG will be listed and summarized by visit and treatment group. The unscheduled visit information will not be included in the summary table.

[figure not shown]
2.11.2 Total Tryptase

[figure not shown]
Total tryptase levels and sampling time will be listed by subject and sampling time point. Post-baseline measurements (i.e. those taken at the time of a suspect hypersensitivity event) will be flagged. A summary table will be provided for baseline values by treatment group. The unscheduled visit information will not be included in the summary table.

2.13 Interim analysis

2.13.1 Planned interim analysis

The first interim analysis (IA1) is planned once all subjects of the CQGE031C2302 and CQGE031C2303 have completed Week 12 (Visit 204) in the first half of the treatment period to evaluate the primary endpoint of retreatment efficacy. Details will be provided by the separate SAP for IA1.

The second interim analysis (IA2) will be performed at the end of the first half of the treatment period at Week 52 (i.e. once all subjects have complete visit 214 or 301, whichever comes first) to evaluate endpoints up to the end of 1 year treatment. Details will be provided by the separate SAP for IA2.

Scopes of IA1 and IA2 are described and summarized in **Table 2-12**.

For the purpose of periodical safety review, independent analyses will be performed for DMC meetings, which will be held at least once for every 6 months. To maintain the treatment blinding until all subjects in this study have completed Week 12 (Visit 204), the outputs for the DMC will be conducted in a semi-blinded manner (using dummy treatment code) prior to the first interim analysis, by the independent statistician and programmer in the separate CRO who are not involved in CSR reporting. Details will be provided by the DMC charter. Outputs to be provided to the DMC will be specified in the separate document.

Additional analyses may be performed to support health authority interactions as necessary.

Due to the early termination of study CQGE031C2302E1, the planned interim analysis IA1 and IA2 will not be performed. A final analysis of all data collected up to last study visit will be performed when all subjects have completed the last study visit.

Table 2-12 Overview of Scope of Interim Analyses 1 & 2

Population/ Analysis /Study Period	Endpoints
Interim analysis I (week 12)	
Analysis: Efficacy Population: ligelizumab retreatment subpopulation Period/time point: TRT1A/Visit204 (Week 12)	
 • proportion of subjects with well-controlled urticaria (UAS7 ≤ 6) at Week 12 • The proportion of subjects with completely controlled disease (UAS7 = 0) at Week 12 • Absolute change from extension study baseline in the UAS7 and its components (ISS7 and HSS7) at Week 12 • Cumulative number of weeks that subjects achieve weekly angioedema activity score (AAS7) = 0 between extension study baseline and Week 12 • Percentage of subjects achieving DLQI = 0-1 at Week 12


Analysis: Safety
 
Population: SAF
 
Period: TRT1A
	
 • TEAE (crude incidence) in TRT1A • TEAE, TESAE, TEAESI (crude incidence) in TRT1A • Related TEAE, TEAEs leading to discontinuation, death,(crude incidence), in TRT1A • Summary of vital signs, by visit, in TRT1A • Summary of lab assessments, by visit, in TRT1A

Interim analysis II (week 52)
	

Analysis: Efficacy
 
Population: self-administer subpopulation, who has at least one self-administration in TRT1B
 
Period/time point: 12 weeks after starting outside-clinic self-admisitration in TRT1B
	
 • The proportion of subjects with well-controlled disease (UAS7 \leq 6), 12 weeks after starting self-administration

Analysis: Efficacy
 
Population:
 
 1) FAS whose preceding study is C2302/2303 (in two subpopulations, by preceding treatment group) 2) FAS 
Period: TRT1
	
 • Proportion of subjects with UAS7 \leq 6 response by visit • Proportion of subjects with UAS7 = 0 response by visit • Proportion of subjects with HSS7 = 0, ISS7 = 0 and UAS7 = 0 response by visit • Absolute and percent change from extension study baseline in HSS7, ISS7 and UAS7 by visit 

Analysis: Safety
 
population:
 
 1) SAF 2) PFS subpopulation (by treatment group + total) 3) Self-administer subpopulation 
period: TRT1
	
 • TEAE, TESAE, TEAESI (crude incidence) • Related TEAE, TEAEs leading to discontinuation, death,(crude incidence) • Summary of vital signs, by visit • Summary of lab assessments, by visit

2.13.2 Unplanned interim analysis

An unplanned interim analysis will be performed to support CSU BLA submission and health authority interactions regarding outside-of-clinic self-administration of ligelizumab with PFS. The safety, efficacy [REDACTED] data available from this study at the time of CSU BLA submission will be provided in a separate abbreviated report. The Outputs shell will be provided in CSR outputs TFL shell.

The pivotal studies (CQGE031C2302/CQGE031C2303) and the extension study will still be ongoing at the time of the unplanned interim analysis, so all outputs will be provided in a blinded fashion. Any team members who are unblinded to the pivotal study treatment group will not participate in the CTT of the extension study.

2.13.2.1 Interim analysis set(s)

The Safety analysis set (SAF), as defined in Section 2.2, including all subjects who received at least one dose of study treatment will be used for all the analyses of this interim analysis.

Three types of administration defined in Table 2-13 are of interest in this interim analysis. The following subpopulations according to those types of administration will be considered in the safety and efficacy analyses for this interim analysis:

- **Outside-of-clinic self-administration:** participants who have at least one outside-of-clinic injection with PFS administered by either the participant herself/himself or a caregiver.
- **Self-administration:** participants who have at least one injection with PFS administered by the participant herself/himself or a caregiver either in clinic or outside of clinic.
- **In-clinic staff-administration:** participants who have all injections with PFS administered in clinic and by the site staff.

Definition of the above three subpopulations only depends on data in the first half of the treatment period. For example, participants who have all injections done in-clinic and by site staff in the first half of the treatment period, and start self-administration in the second half of the treatment period would belong to the in-clinic staff-administration subpopulation for the purpose of this interim analysis.

Table 2-13 Definition of type of administration

Type of administration	Definition
Outside-of-clinic self-administration	Outside-of-clinic injections with PFS administered by either the participant herself/himself or a caregiver
Self-administration	Injections with PFS administered by the participant herself/himself or a caregiver either in clinic or outside of clinic

In-clinic staff-administration	Injections with PFS administered in clinic and by the site staff
--------------------------------	--

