- subjects starting treatment at Visit 201 (Week 0) and subsequent visits 202 and 203 (Weeks 4 and 8) will be monitored at the site for 2 hours after administration, and for 30 minutes for all remaining visits as long as their treatment is not interrupted during the full 104 week treatment period; and
- subjects who are entering the second half of the treatment period (Visit 214, Week 52) from the second observation period will be monitored at the site for 2 hours after administration for the first three Visits 214, 401 and 402 (Weeks 52, 56 and 60).
 - All subjects receiving treatment in clinic will remain in clinic for a 30 min observation period for all remaining treatment visits.
 - All subjects self-administering ligelizumab in their out-of-clinic setting should remain in a quiet environment for 30 minutes after administration for self-observation for all remaining treatments.

Self-administration outside of clinic

PFS injections should only be administered by adults or adult caregivers.

Subject will be given the option to start self-administration at Visit 204 (Week 12) or Visit 403 (Week 64). During these visits subjects who are willing to self-administer, should be evaluated according to the below criteria. If the criteria are satisfied, then the IFU will be provided and the subjects or caregiver who will perform the administration will undergo training.

[figure not shown]
The clinical criteria for self-administering ligelizumab is below:

- The subject should not have experienced any severe/serious hypersensitivity reactions (including during the preceding studies)
- The subject should know how to recognize symptoms/signs of severe hypersensitivity reactions
- The subject should be capable and willing to self-administer ligelizumab

For the first and second use of PFS at Visit 204 (Week 12) / Visit 403 (Week 64) and Visit 205 (Week 16) / Visit 404 (Week 68) respectively, the self-injection will take place as a site staff assisted injection i.e. with the help of the site staff performing the injection steps. At the third use of PFS at Visit 206 (Week 20) / Visit 405 (Week 72), the self-injection will take place under supervision however without the help of the site staff, i.e. the site staff only observes and does not help in performing the injection steps. The training for each injection, be it assisted or under supervision, will be provided individually by the site staff to the subject.

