To investigate the safety and tolerability of ligelizumab 120 mg in all subjects who will be self-administered, a summary table will be provided to include the information after the first dose using self-administration. Subjects who move from self-administration back to in-clinic administration during the study, they will be included in this analysis if majority (>50%) of drug use is based on self-administration.

SAE summaries will be provided in a similar manner.

Vital signs

Analysis of the vital sign measurements using summary statistics for the change from baseline for each post-baseline visit will be performed. These descriptive summaries will be presented by vital sign and treatment group. Change from baseline will only be summarized for subjects with both baseline and post-baseline values. Subjects with notable vital signs as defined in [Appendix 1](#) will be listed.

12-lead electrocardiogram (ECG)

All ECG data will be listed by treatment group, subject and visit/time, abnormalities will be flagged. Summary statistics will be provided by treatment and visit/time.

Clinical laboratory evaluations

The summary of laboratory evaluations will be presented for 2 groups of laboratory tests (hematology and serum chemistry). Descriptive summary statistics for the change from baseline to each study visit will be presented. These descriptive summaries will be presented by laboratory test and treatment group. Change from baseline will only be summarized for subjects with both baseline and post baseline values. Shift tables using the low/normal/high/ (low and high) classification will be used to compare baseline to the worst on-treatment value.

Other safety evaluations

[REDACTED]

[REDACTED]

[figure not shown]
[REDACTED]

[figure not shown]
Resource utilization

Data relating to resource utilization will be used for the purpose of economic evaluation and will be carried out and reported as a separate activity.

[figure not shown]

[figure not shown]

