2.8.1.2 Crude and Exposure-Adjusted Incidence Rate

The crude incidence rate is defined as the percentage of subjects with a specific adverse event divided by the total number of subjects in each study group.

In a long-term follow-up of the patients, the crude incidence rate might not be a correct measure because it does not include the individual subject's total exposure time in the calculation. As described in **Table 2-10**, the exposure-adjusted incidence rate (EAIR) will be provided for the safety analysis in certain study periods in addition to the crude rate.

The EAIR is defined as the number of subjects with a specific event divided by the total exposure-time among the subjects in the study group. That is, the EAIR is calculated as:

$EAIR = n / \sum t_i$, where n is the number of subjects having the i^{th} type event, and t_i is a subject's exposure time until having an i^{th} type event. If a subject has multiple events of the i^{th} type, the t_i is the time of the first event of that type. For a subject having no event of the i^{th} type, the t_i is the last follow-up time for that subject. The total exposure time of all subjects in a treatment group is $\sum t_i$. The EAIR is interpreted as the number of events occurring in a population per unit time. The exact Poisson 95% confidence interval for the EAIR will be provided as well, where

an exact $100*(1-\alpha)\%$ confidence interval will be derived as follows (Garwood 1936, Sahai and Khurshid 1993):

- Lower confidence limit $L = \frac{0.5C_{\alpha/2,2n}}{\sum t_i}$ for $n>0$, 0 otherwise,
- Upper confidence limit $U = \frac{0.5C_{1-\alpha/2,2n+2}}{\sum t_i}$,

where $C_{\alpha,k}$ is the α th quantile of the Chi-square distribution with k degrees of freedom.

Whenever applicable, exposure adjusted incidence rates will be provided for the type as below:

1. TEAE and TESAE: Primary SOC level and preferred term level
2. Treatment emergent AE of special interest: up to SMQ level 5

When calculating EAIR for AESI of cardiovascular and cerebrovascular (CCV) and malignancy, the adverse event and exposure time both consider the entire study period after the first study treatment.

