2.13.2.5.1 General information

Only treatment emergent adverse events (TEAEs) will be considered. All TEAEs reported will coded using MedDRA terminology and summarized by primary System Organ Class (SOC) and Preferred Term (PT) in the overall population and the subpopulations defined in Section 2.13.2.1.

Non-treatment emergent AEs by study period (including observation period 1) will only be listed and not further summarized.

TEAEs will be summarized by actual received treatment, in relevant treatment periods (see Table 2-15) for each subpopulation defined in Section 2.13.2.1.

TEAEs are defined as:

- Events starting after the first dose of study treatment (ligelizumab) in the extension study and within 16 weeks of last dose of study treatment
- Events present prior to the first dose of study treatment (ligelizumab) in the extension study but:
 - increase in severity based on preferred term (e.g. worsening of headache),
 - same PT but increased severity (e.g. from mild to moderate),
 - same PT but increase in seriousness (from non-serious AE to SAE; if already a SAE from medically significant to life-threatening/fatal)

Within a specific treatment period, a subject with multiple AEs within a primary system organ class will be counted only once for the primary SOC, with the greatest severity at the system organ class level displayed.

The following Treatment emergent AEs of special interest (TEAESIs) defined in the compound-level electronic Case Retrieval Strategy (eCRS) will be presented up to SMQ level 5. The search criteria in the latest eCRS and the corresponding MedDRA version at the database lock will be used for reporting:

- Hypersensitivity reactions (including anaphylaxis)
- Injection site reactions
- Serum sickness

For AESIs with adjudication, separate listing(s) will be provided based on the adjudicated results.

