2.13.2.8 Overview of unplanned interim analysis

Table 2-15 Overview of unplanned interim analysis

Population/ Analysis /Study Period	Endpoints

Analysis: Efficacy
 
Population:
 
SAF
 
Outside-of-clinic self-administration subpopulation
 
Self-administration subpopulation
 
In-clinic staff-administration subpopulation
 
Study period:
 
TRT1
	
 • Proportion of subjects with well-controlled urticaria (UAS7 ≤ 6) by visit • The proportion of subjects with completely controlled disease (UAS7 = 0) by visit • The proportion of subjects with ISS7 = 0 by visit • The proportion of subjects with HSS7 = 0 by visit • Absolute change from extension study baseline in the UAS7 and its components (ISS7 and HSS7) by visit 
█ [REDACTED]

Analysis: Safety
 
Population:
 
SAF
 
Outside-of-clinic self-administration subpopulation
 
Self-administration subpopulation
 
In-clinic staff-administration subpopulation
 
Study period:
 
Week 0—12 in TRT1
 
Week 12—24 in TRT1
 
Week 24 onwards up to interim data cut off
 
Entire study up to interim data cut off
	
The crude incidence and exposure adjusted incidence will be provided for:
 
 • TEAE • Study treatment related TEAE • TESAE • TEAESI • TEAEs leading to discontinuation 
Other:
 
 • Listing of TEAEs leading to drug interruption • Crude incidence of TEAE by severity • Listing of adjudicated AE

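### In the self-administration interim, home-group members must reach Week 24 to qualify, so the group's entire-study rate of adverse events leading to discontinuation is too low beside the in-clinic group

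*SAP*

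**What the plan says.** The unplanned interim is meant to support a licence submission and "health authority interactions regarding outside-of-clinic self-administration of ligelizumab with PFS" (SAP 2.13.2). SAP 2.13.2.1 forms its groups from injections given in the first half of the treatment period:

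- Home (outside-of-clinic self-administration): "participants who have at least one outside-of-clinic injection with PFS administered by either the participant herself/himself or a caregiver".
- In-clinic staff: "participants who have all injections with PFS administered in clinic and by the site staff".
- A wider self-administration group also takes in subjects who self-injected in the clinic only.

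Protocol 4.2 starts PFS dosing at Week 12 and home dosing at Week 24. Protocol 6.7.2 sets a suitability criterion, checked at Week 12 when training begins: "The subject should not have experienced any severe/serious hypersensitivity reactions (including during the preceding studies").

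On safety, SAP 2.13.2.5.1 says: "TEAEs will be summarized by actual received treatment, in relevant treatment periods (see Table 2-15) for each subpopulation defined in Section 2.13.2.1". Table 2-15 gives four windows: Weeks 0-12, Weeks 12-24, Week 24 onwards, and "Entire study up to interim data cut off". Each gets crude incidence and an exposure-adjusted incidence rate (EAIR), including for TEAEs leading to discontinuation. SAP 2.8.1.2 sets the crude denominator group by group: "The crude incidence rate is defined as the percentage of subjects with a specific adverse event divided by the total number of subjects in each" [group].

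The planned self-administration safety analysis counts differently. In Protocol 12.5.2, "a summary table will be provided to include the information after the first dose using self-administration", and SAP 2.8.1.3 makes that the first out-of-clinic dose. SAP 2.8.1.3 then says self-administration safety has been evaluated at the interim and will not be repeated. In Table 2-16 the self-administration group has an efficacy row only.

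**The concern.** Membership of the home group depends on something that happens at Week 24 or later, yet three of the four windows count time before that. A home subject cannot have stopped treatment before Week 24. A subject whose PFS doses were all given by staff and who stops in Weeks 12-24 stays in the in-clinic group. For discontinuation events, the two columns therefore differ even if the setting of the injection has no effect.

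The suitability criterion adds selection in the same direction. A severe or serious hypersensitivity reaction known at the Week 12 check keeps a subject out of home dosing. Hypersensitivity is one of the interim's events of special interest.

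At stake is the only safety analysis of a stated secondary objective. A low home rate in the entire-study row could be credited to home dosing when it comes from how the group was formed.

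**Working it through.** The documents give no event rate for this interim, so there is no plan figure to reproduce. The question is what the display would show if setting had no effect.

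**Inputs from the documents**
- First home dose at Week 24, and first PFS dose at Week 12 (Protocol 4.2). Week 24 is Day 24 × 7 + 1 = 169, which matches Visit 207 in Protocol Table 8-1.
- EAIR is subjects with an event divided by total exposure time (SAP 2.8.1.2).

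**Assumptions**
- A constant hazard h of stopping for an adverse event, the same in both groups: h = -ln(1 - p)/52 per week, with p = 2%, 5% or 10% over 52 weeks.
- Follow-up T of 36 or 52 weeks in both groups.
- An in-clinic subject needs at least one PFS dose, so must reach Week 12.

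**Share of counted time with no possible stop in the home group:** 24/52 = 46% and 24/36 = 67%.

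**Entire-study EAIR per week**
- Home: (1 - e^(-h(T-24))) / [24 + (1 - e^(-h(T-24)))/h]
- In-clinic: (1 - e^(-h(T-12))) / [12 + (1 - e^(-h(T-12)))/h]

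For p = 5% and T = 52, h = 0.000986:
- Home: 0.02724 / (24 + 27.62) = 0.000528 per week, or 2.74 per 100 subject-years (× 5,200).
- In-clinic: 0.03869 / (12 + 39.22) = 0.000755 per week, or 3.93 per 100 subject-years.
- The common true rate is 5,200h = 5.13.

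| p over 52 weeks | T (weeks) | Home EAIR | In-clinic EAIR | Ratio |
|---|---|---|---|---|
| 2% | 52 | 1.09 | 1.55 | 0.70 |
| 5% | 52 | 2.74 | 3.93 | 0.70 |
| 10% | 52 | 5.60 | 8.03 | 0.70 |
| 2% | 36 | 0.67 | 1.34 | 0.50 |
| 5% | 36 | 1.70 | 3.41 | 0.50 |
| 10% | 36 | 3.48 | 6.97 | 0.50 |

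The ratio hardly depends on p. For small h it is close to (T - 24)/(T - 12), that is 28/40 = 0.70 and 12/24 = 0.50. Crude incidence behaves alike: at p = 5% and T = 52, 2.7% against 3.9%.

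**Weeks 12-24 alone:** no home subject can stop. The in-clinic risk is 1 - e^(-12h) = 0.5%, 1.2% or 2.4%.

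**Subjects with no PFS dose.** The definitions do not place them. If they counted as in-clinic, and half of subjects chose home dosing, the EAIR ratio would fall to 0.43-0.44 at 52 weeks and about 0.25 at 36 weeks.

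**TEAEs in general.** In a simulation of 2,000,000 subjects (60% risk over 52 weeks, 15% other drop-out, no true difference), TEAEs that never cause stopping gave an EAIR ratio of 1.00. The crude ratio was 1.02, or 1.09 with no-PFS subjects counted as in-clinic, so slightly against home dosing. If 5% of TEAEs cause stopping, the EAIR ratio is 0.99; if 20% do, it is 0.96.

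**Week 24 onwards, crude.** If a fraction f of in-clinic subjects never enters the period but stays in the denominator, a true rate r shows as r(1 - f). With r = 40% and f = 10%, 20% or 30% (all assumed), the in-clinic column shows 36%, 32% or 28%, while the home column is not diluted.

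**After the fix.** Counting both groups from Week 24 among subjects still on treatment, the discontinuation EAIRs are equal (5.13 and 5.13 at p = 5%). In simulation, first TEAEs after Week 24 have ratios of 0.998 to 1.007.

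**The case against.** The strongest reply is that Table 2-15 already has a Week 24 onwards row. SAP 2.13.2.3.3 starts that exposure at the first PFS injection from the Week 24 visit, and SAP 2.13.2.5.2 ties the event count to the period. The EAIR in that row is therefore largely sound. This stands, and it limits the problem to the other windows and to the crude figure. The crude figure is affected only if the study group means the whole subpopulation; SAP 2.8.1.2 does not limit it to those who entered the period. The disposition and exposure tables do let a careful reader see who entered.

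A reader might infer that home dosing is made to look safer throughout. The documents do not support that. For TEAEs that do not cause stopping, the EAIR is about unbiased, and crude figures can run against home dosing.

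A reader might also infer that all severe hypersensitivity in Weeks 0-12 lands in the in-clinic group by rule. It does not. That group is defined by PFS injections, so a subject who reacts and stops before Week 12 has no clearly stated group. The same gap means the Weeks 0-12 discontinuation contrast depends on where such subjects are placed. The criterion also describes who is eligible for home use, so its effect is not purely a counting artefact.

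Finally, no test or contrast between modes is specified, development in this indication has been discontinued, and the interim output exists. These points lower the consequence. They do not remove it: parallel columns invite comparison, and no other self-administration safety analysis is planned.

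**Conclusion.** The point holds in a limited form. For TEAEs leading to discontinuation, the Weeks 12-24 and entire-study rows give the home group a built-in advantage. With no true difference, the entire-study EAIR ratio is about 0.70 at 52 weeks and 0.50 at 36 weeks. The direction follows from the definitions. The size rests on a constant, equal hazard, equal follow-up and at least one PFS dose for in-clinic subjects, but hardly on the assumed rate. The home rate before Week 24 is near zero rather than exactly zero, because an event that starts earlier can lead to a later stop.

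Severe or serious hypersensitivity is affected in the same direction, but only in part, and no size can be given. The crude Week 24 onwards figure can err the other way.

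**What to change.** In SAP 2.13.2 and Table 2-15:

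1. Make Week 24 onwards the only home versus in-clinic safety display. Include subjects still on treatment who received the Week 24 dose or, if it was missed, the next one.
2. Fix each subject's group by the mode of that dose, and count events and exposure from it.
3. Use subjects entering the period as the crude denominator, and say so.
4. Show Weeks 0-12, Weeks 12-24 and the entire study for the safety set only.
5. State where subjects with no PFS dose belong.
6. If events are also to be assigned to the mode of the most recent injection, give that as a separate supportive table. It is a different analysis from step 2.
7. Use the Week 24 table to answer the self-administration safety objective in Protocol 12.5.2, and amend SAP 2.8.1.3, which says this analysis will not be repeated.

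No new data are needed. The costs are SAP wording, re-programming of output already produced, and fewer events per table because time before Week 24 is dropped. As the interim has been run, the corrected table should be labelled a re-analysis in the study report.
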